The next trial, currently only available as an abstract, involved 10 patients with failed back surgery treated by an anesthesiology-trained pain physician (Abdi, Lakkimsetty et al. 2011). While it only noted a 28% mean pain reduction, there were patients on this trial who had substantial relief after multiple other therapies had failed to provide benefit. The author of this abstract (verbal communication, May 2015) notes that there are three reasons why his success rate might have been relatively low: 1) he had limited operator experience; 2) he included study subjects with multifactorial intractable pain despite intensive polypharmacy; and 3) treatment while adjuvant anticonvulsants were continued. Empiric observations have suggested less than optimal outcomes if these medications are not discontinued prior to treatment.

Marineo and colleagues published the first randomized controlled trial in 2011, which involved 52 patients with chronic neuropathic pain related to postsurgical causes, postherpetic neuralgia, or spinal cord stenosis (Marineo, Iorno et al. 2011). Scrambler Therapy was compared to a control arm that utilized standard pharmacologic guideline-based recommendations, including frequent phone calls to modify analgesics. The pain

[figure not shown]

Figure 2. VAS pain before and after each treatment session.

reduction after finishing 10 days of treatment was 28% in the control group (pain scores dropped from 8.0 to 5.8 out of 10) compared to a 91% reduction with the Scrambler group (pain scores dropped from 8.1 to 0.7; $p < 0.0001$; Figure 3). Pain scores in the control arm were 5.7 and 5.9 at two and three months, respectively, as opposed to 1.4 and 2.0 in the Scrambler group ($p < 0.0001$). Pain drug consumption, including opioids, antidepressants, and anticonvulsants, decreased by 72% in the Scrambler group. Allodynia also was reduced in the Scrambler patients, from 77% at baseline to 15% at three months. Benefit was obtained relatively equally amongst patients of all of the three diagnostic categories.

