2.3 Goal 3 Efficacy

Evaluate whether Scrambler therapy, compared to TENS therapy, can decrease the use of pain medication for CIPN.

Hypothesis 3: Pain medication and morphine oral equivalent dose (MOED) daily amounts will decrease more in the group receiving Scrambler therapy, compared to those who received TENS therapy.

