- 3.23 Existing implantable medical electronic devices, life-supporting medical devices, and medical monitoring devices.
Note: Metal implants for orthopedic repair, e.g. pins, clips, plates, cages, joint replacements are allowed, as are central venous access devices.
- 3.24 History of myocardial infarction or ischemic heart disease within the past six months.
- 3.25 History of epilepsy, brain damage, use of anticonvulsants for seizure prevention, concurrently using ketamine, symptomatic brain metastases.
- 3.26 Skin conditions such as open sores that would prevent proper application of the electrodes.
- 3.27 Other medical or other condition(s) that in the opinion of the investigators might compromise the objectives of the study.
- 3.28 Currently receiving gabapentin or pregabalin and not willing to be weaned off of these medications prior to Scrambler therapy initiation.
Note: It is OK to continue these medications in patients who are receiving TENS. (See [Appendix I](#)).
- 3.29a History of peripheral neuropathy prior to receiving neurotoxic chemotherapy.
- 3.29b Prior treatment with Scrambler therapy.

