9.2 Gabapentinoid use

Patients should not receive gabapentinoids (e.g. Neurontin®, Lyrica®) during treatment with Scrambler therapy. If patients are on gabapentinoids at the time of registration and are randomized to Scrambler therapy, they must be weaned off prior to receiving Scrambler therapy.

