9.3 Other pain treatment

Other pain treatments are allowed if the pain is not satisfactorily controlled. All pain treatments and pain-related medications will be recorded.

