16.32 Secondary efficacy endpoints

Perceived treatment efficacy from the Subjective Global Impression of Change instrument (Appendix IXA and B) will be summarized (median and range for impression of change and frequency for preference) by arm and compared

(Wicoxon rank-sum test for impression of change and Chi-square test for preference) between treatment arms.

EORTC CIPN20 scores and changes in scores will be summarized (mean, sd, median, range) at each time point by arm and will be compared between arms using two-sample t-tests.

- 16.33 Goal: Evaluate the tolerability of Scrambler therapy and compare it to TENS therapy, in this population.

Frequency and type of toxicities occurred during therapy will be summarized by treatment arm and compared between arms using Fisher-exact test.

- 16.34 Goal: Evaluate whether Scrambler therapy, compared to TENS therapy, can decrease the use of pain medication for CIPN.

Type and frequency of analgesic used will be summarized by treatment arms and will be compared using Fisher-exact test.

- 16.35 Goal: Explore whether mRNA gene expression changes are similar to that previously reported by Starkweather et al.

In a descriptive manner, the gene expression will be compared to what was previously reported.

- 16.36 Goal: Explore whether Scrambler therapy will change fMRI.

Changes in fMRI following Scrambler therapy will be described in the subset of patients selected for this component of the study.

- 16.37 Descriptive statistics will be used for the data from Quantitative Sensory Testing.

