Appendix I Patient instruction sheet for tapering gabapentin and pregabalin

Tapering of gabapentin or pregabalin will preferably occur over two weeks. Lower doses may be tapered over one week to accommodate patient availability with approval of [name]. During first week of taper, drug will be reduced approximately 25% for 3-4 days, then an additional 25% so that the drug has been reduced by approximately 50% by the end of the first taper week. Drug will continue to be reduced during the second week every few days until the final dose is taken the evening prior to treatment. Patient provider or [name] will need to be contacted if different doses of pills are needed. Patients will be instructed on potential symptoms of withdrawal and be asked to contact study staff if symptoms are experienced, as the taper may need to be adjusted. The decision of which dose to begin tapering (morning, noon, evening) will be decided between patient and study staff.

Patient Form

Gabapentin/Pregabalin (circle one)	mg	mg	mg	mg
Day/Date				
1= / /	pills	pills	pills	pills
2= / /	pills	pills	pills	pills
3= / /	pills	pills	pills	pills
4= / /	pills	pills	pills	pills
5= / /	pills	pills	pills	pills
6= / /	pills	pills	pills	pills
7= / /	pills	pills	pills	pills
8= / /	pills	pills	pills	pills
9= / /	pills	pills	pills	pills
10= / /	pills	pills	pills	pills
11= / /	pills	pills	pills	pills
12= / /	pills	pills	pills	pills
13= / /	pills	pills	pills	pills
14= / /	pills	pills	pills	pills
Day 1 of Treatment	0 pills	0 pills	0 pills	0 pills

Potential symptoms of gabapentin withdrawal may include nausea, insomnia, restlessness, agitation, anxiety, disorientation, confusion, light sensitivity, sweating, headaches, palpitations, chest pain, and flu-like symptoms.

**Appendix IIA Peripheral Neuropathy Questionnaire for Upper Extremity Neuropathy
(Used for Eligibility)**

Initials _____
Study # _____
Date _____
Day _____

How much of a problem has **pain** in your fingers or hands been **in the past week**?

0	1	2	3	4	5	6	7	8	9	10
No pain in fingers and/or hands										Pain in fingers and/or hands as bad as you can imagine

How much of a problem has **tingling** in your fingers or hands been **in the past week**?

0	1	2	3	4	5	6	7	8	9	10
No tingling in fingers and/or hands										Tingling in fingers and/or hands as bad as you can imagine

**Appendix IIB Peripheral Neuropathy Questionnaire for Lower Extremity Neuropathy
(Used for Eligibility)**

Initials _____
Study # _____
Date _____
Day _____

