Appendix VIII Patient Analgesic Use Questionnaire

Initials _____
Study # _____
Date _____
Day _____

Please list all pain medications (drug, dose, and quantity) used in the past 24 hours.

Drug	Unit Dose	Quantity over past 24 hours
Example Acetaminophen or Tylenol	500 mg	4 pills

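### Section 16.34 does not analyse the decrease in daily opioid-equivalent dose that Hypothesis 3 predicts, and does not set aside gabapentinoids, which are barred during Scrambler therapy but allowed on TENS

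*Combined protocol and SAP*

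**What the plan says.** Section 2.3 (Goal 3) asks whether Scrambler therapy reduces use of pain medication. Its hypothesis concerns amounts: "Pain medication and morphine oral equivalent dose (MOED) daily amounts will decrease more in the group receiving Scrambler therapy" than in the TENS group.

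Section 16.34 restates the goal and gives its only analysis: "Type and frequency of analgesic used will be summarized by treatment arms and will be compared using Fisher-exact test". MOED is not mentioned there or anywhere else outside Hypothesis 3.

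The form that supplies the data, Appendix VIII, is detailed enough for a daily amount: "Please list all pain medications (drug, dose, and quantity) used in the past 24 hours". The test schedule in section 4.0 has it completed on Day 1, daily for 14 days and weekly for 8 weeks.

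The gabapentinoid rules differ by arm. Section 9.2 bars these drugs during Scrambler therapy and says of patients already taking them that "they must be weaned off prior to receiving Scrambler therapy". The note to criterion 3.28 says of the other arm: "It is OK to continue these medications in patients who are receiving TENS". Appendix I describes the taper, with the last dose on the evening before treatment: "Tapering of gabapentin or pregabalin will preferably occur over two weeks". Section 9.3 leaves other pain treatment open to both arms and has all of it recorded: "Other pain treatments are allowed if the pain is not satisfactorily controlled".

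**The concern.** There are two separate problems.

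First, the test does not match the hypothesis. The hypothesis concerns a decrease in daily amount. A Fisher exact test on type and frequency compares counts of patients. Section 16.34 does not define frequency, but a Fisher test implies number of users. On that reading a patient who cuts the dose without stopping counts the same as one who changes nothing. Section 16.32 does specify changes in score at each time point for the CIPN20, so change analyses are written in where they are intended.

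Second, the protocol itself creates an arm difference in one class of pain drug. Section 16.34 neither defines analgesic nor excludes gabapentinoids. Including them is a natural reading: Appendix VIII asks for all pain medications, and section 1.4, describing an earlier randomised trial, counts anticonvulsants: "Pain drug consumption, including opioids, antidepressants, and anticonvulsants, decreased by 72% in the Scrambler group". If they are included, a comparison of use during treatment can favour Scrambler through the weaning rule alone. That result would look like support for Hypothesis 3 and could feed into the larger study that section 16.5 has in view.

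**Working it through.** The plan states no figure for this goal, so there is none to reproduce.

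**Inputs.** 25 patients per arm (section 16.5). Two-sided Fisher exact test at 0.05; the level is an assumption, since none is set for Goal 3. Gabapentinoid use is 0 on Scrambler during treatment (section 9.2) and g on TENS. Other-analgesic use is o in both arms, with no device effect. The documents give neither g nor o; both are assumed over a range. Equating g with use at entry assumes that every TENS user continues.

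**1. Gabapentinoids tested as a drug type.** For 0/25 versus k/25, the two-sided p-value is 2 × C(25,k) / C(50,k). For k=6 this is 2 × 177,100 / 15,890,700 = 0.022.

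| TENS users k | 3 | 4 | 5 | 6 | 7 | 8 |
|---|---|---|---|---|---|---|
| p | 0.235 | 0.110 | 0.0502 | 0.022 | 0.010 | 0.004 |

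Significance therefore needs k ≥ 6. With k ~ Binomial(25, g), the chance of p<0.05 from the protocol rule alone is P(k ≥ 6):

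| g | 10% | 15% | 20% | 30% |
|---|---|---|---|---|
| P(p<0.05) | 0.033 | 0.162 | 0.383 | 0.807 |

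**2. Any-analgesic use.** If other-analgesic and gabapentinoid use are independent, the Scrambler rate is o and the TENS rate is 1 − (1−o)(1−g). For o=0.2 and g=0.2 the TENS rate is 1 − 0.8 × 0.8 = 0.36. Enumerating all pairs of binomial counts gives P(p<0.05):

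| o | g=0 | g=10% | g=20% | g=40% |
|---|---|---|---|---|
| 20% | 0.022 | 0.052 | 0.150 | 0.571 |
| 40% | 0.030 | 0.047 | 0.100 | 0.335 |
| 60% | 0.030 | not computed | 0.054 | 0.147 |

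The g=0 column is also the result of setting gabapentinoids aside: the false-positive rate is then 2 to 3%.

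**3. Dose reductions.** Suppose m patients per arm take the same opioid dose. All m on Scrambler cut it by two thirds without stopping, and nobody on TENS changes. User counts stay at m/25 versus m/25, so Fisher p=1.00 for every m. In a rank test of change, m Scrambler patients share one negative value and all other patients have zero. With only two distinct values, the exact permutation p-value of the rank-sum test equals Fisher for m/25 versus 0/25, so the formula in step 1 applies: p=0.235 (m=3), 0.0502 (m=5) and 0.0006 (m=10).

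**4. Direction depends on the baseline.** Use during treatment, or change from registration, is pushed towards less medication on Scrambler. Change from Day 1 starts after the taper, so it hides that drop and leaves mainly TENS patients able to show a gabapentinoid decrease. Section 16.34 names neither baseline nor time point, so the direction is left open.

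**The case against.** The strongest reply is that the gabapentinoid half is conditional and its larger figures are illustrative. Section 16.34 does not say these drugs are included; recording them does not make them part of the test, and the 72% figure describes how another trial counted drugs. Criterion 3.28 excludes users unwilling to be weaned before randomisation, which lowers use in both arms. The TENS rule is permissive: if half of TENS users continued, 20% use at entry would act as g=10% (0.03 rather than 0.38) and 30% as g=15% (0.16 rather than 0.81). A separate gabapentinoid row would also show the protocol rule plainly. The pooled comparison is the one more likely to mislead, and there the distortion is small at low use.

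Those points stand as limits on size. They do not remove the defect: the text allows the drugs to be counted, and their use during treatment is set by allocation.

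On the dose half, comparing post-treatment use between randomised arms is a valid contrast, and lack of a change score is not by itself an error. That is right, but the planned contrast still contains no amount, which is what the hypothesis predicts. The dose example is deliberately stark, and even there the rank test misses 0.05 with 3 or 5 opioid users per arm. With few opioid users, no analysis of MOED will have much power.

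Finally, section 16.5 attaches its p<0.05 interpretation to the primary endpoint, so no stated decision rests on Goal 3. That limits the consequence, although the trial is meant to inform later hypotheses.

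**Conclusion.** The concern holds in both parts. The planned test cannot detect the predicted decrease in daily amount when patients reduce a dose without stopping, although the data to do so are already collected. This rests on reading frequency as number of users, which the Fisher test implies.

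The gabapentinoid rules can also produce an apparent Scrambler advantage in use during treatment with no device effect. The size depends on use rates that the documents do not give. It is negligible at 10% use. At 20% it is 0.38 for a drug-type test and 0.05 to 0.15 for any-analgesic use, the latter depending on other-analgesic use of 60% down to 20%. All these figures assume that TENS users continue; fewer continuing means less distortion. MOED counts opioids, so the rules touch it only indirectly.

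The primary endpoint and sample size are unaffected. The plan should be changed, but only the interpretation of a secondary goal is at risk. No view is taken here on the gabapentinoid rules themselves.

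**What to change.** Rewrite section 16.34 as follows.

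- Derive daily MOED from the opioid entries in Appendix VIII, using a named conversion table.
- Compare change from Day 1 to the end of the initial two-week treatment, and to Week 8, between arms by Wilcoxon rank-sum test. Use exact or permutation p-values, because opioid non-users contribute tied zeros.
- Define analgesic and frequency, and summarise non-opioid analgesics by arm.
- Report gabapentinoids separately. Leave them out of the between-arm test during the treatment period, because their use then depends on allocation, and describe their Week 8 use without a test.
- Keep any analysis restricted to baseline opioid users descriptive.
- State two limitations. Day 1 follows the taper for weaned Scrambler patients, although a 24-hour recall form may still list the last evening dose. Opioid use may itself respond to gabapentinoid withdrawal, since section 9.3 allows other pain treatment.

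The cost is SAP wording and a standard opioid conversion. No new form, visit or patient is needed.

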16.4 Accrual and Duration of Study

We plan to accrue 50 patients on this trial. Given our previous experience with requests for Scrambler Therapy, we estimate an accrual rate of 3 patients per month so that we expect to complete accrual within 1.5 years. With a maximum total time of treatment and observation of 5 months, the expected total duration of the study is 2 years.

16.5 Sample size

The sample size of 50 patients (25 per arm) in this prospective randomized study is mostly determined by feasibility. This study is not designed as a confirmatory study, hence, not powered as such. The primary purpose of this study is to estimate the effect of scrambler therapy for the treatment of CIPN which will inform hypothesis formulation for future studies. If the data from this study suggest a clinically non-ignorable effect of scrambler therapy compared to TENS therapy, we will plan for a larger study to confirm its benefit. However, if the data from this trial show a very large difference in changed pain scores between the two arms, such that the primary endpoint is positive with a p-value of less than 0.05, we will interpret this outcome as evidence that Scrambler therapy is better than TENS therapy, or vice-versa, depending on which arm is doing better.

More than 45% of patients in Pachman et al.'s study experienced treatment effect (50% or more reduction in symptom scores) after 2 weeks of scrambler therapy (Pachman, Weisbrod et al. 2014). This estimate includes patients who were enrolled early in the trial who did not respond to the treatment as well as the later cohort, potentially due to the study team's inexperience in the beginning of the trial. With the current level of experience, we expect a much higher percentage of reduction in patients' symptom scores after scrambler therapy in this trial. The likelihood of detecting an improvement of 30% or more after scrambler therapy compared to TENS is high with a sample size of 25

patients per arm. Table 16.51 shows the minimum detectable improvement with at least 80% power at a one-sided .05 significance level for various plausible scenarios with 25 patients per arm.

Table 16.51. Minimum Detectable Improvement with 80% power at a one-sided 0.05 significance level

Proportion of patients achieving 50% or more reduction in symptom scores from baseline		Minimum Detectable improvement	Power (%)
TENS	Scramber		
.05	.32	.27	80
.10	.40	.30	80
.20	.54	.34	81
.30	.65	.35	81
.40	.75	.35	82

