2.0 Goals

2.1 Goal 1 Efficacy

Evaluate the efficacy of Scrambler therapy compared to TENS therapy for pain and/or tingling related to CIPN.

Hypothesis 1: Scrambler therapy will improve pain related to chemotherapy induced neuropathy more than TENS therapy.

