16.3 Analysis Plan**16.31 Primary endpoint**

Evaluate the efficacy of Scrambler therapy compared to TENS therapy for pain and/or tingling related to CIPN.

The main efficacy endpoint is defined as achieving 50% reduction in pain or tingling from baseline. At enrollment, patients will be asked to select either pain or tingling as their primary symptom of concern. Allowing the patients to select their main symptom (pain or tingling) is reasonable since the scores and the patterns of reduction were similar for pain and tingling after Scrambler therapy as shown by Pachman et al. (Pachman, Weisbrod et al. 2014)

Descriptive statistics (mean, sd, median, range) of pain and tingling scores and changes pre- and post-treatment scores will be summarized and the percentage of pain and tingling reduction from baseline will be calculated for each timepoint, separately by treatment arm. Longitudinal plots of scores by arm will be provided. The frequency and percentages of patients who achieved more than 50% reduction in pain and/or tingling scores after 2 weeks of therapy (scores from the last treatment day compared to the pre-treatment data, using the question related to average symptom [pain or tingling, whichever the patient chose when entering the study] over the previous 24 hours) and after 8 weeks of observation (scores from Week 8 form) from baseline (scores from Day 1 pre-treatment form) will be summarized by treatment arm and will be compared between arms using a Chi-square test (or Fisher-exact test as appropriate).

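### Table 16.51 gives power at one-sided 0.05, but the p<0.05 conclusion can favour either arm and its sidedness is never stated; read as two-sided, the table's 80-82% power is 70-72%

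*Combined protocol and SAP*

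**What the plan says.** Section 16.5 sets 50 patients, 25 per arm, mainly on feasibility, and states: "This study is not designed as a confirmatory study, hence, not powered as such". It then keeps a formal conclusion in reserve. If the difference is very large, "such that the primary endpoint is positive with a p-value of less than 0.05", then "we will interpret this outcome as evidence that Scrambler therapy is better than TENS therapy, or vice-versa, depending on which arm is doing better".

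The next paragraph introduces Table 16.51, which "shows the minimum detectable improvement with at least 80% power at a one-sided .05 significance level". The table lists TENS response rates of .05, .10, .20, .30 and .40 with detectable improvements of .27, .30, .34, .35 and .35, at a stated power of 80, 80, 81, 81 and 82%. The text before it says: "The likelihood of detecting an improvement of 30% or more after scrambler therapy compared to TENS is high".

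Section 16.31 names the test. Response proportions "will be compared between arms using a Chi-square test (or Fisher-exact test as appropriate"). It gives no significance level, no sidedness and no condition for moving to Fisher's test. Hypothesis 1 in section 2.1 is directional: "Scrambler therapy will improve pain related to chemotherapy induced neuropathy more than TENS therapy".

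**The concern.** One section holds a power table for a test in one direction and a decision rule that works in both. If the p-value is two-sided, the printed power belongs to a different and easier test. If it is one-sided in favour of Scrambler, no value of it can support TENS, and the either-arm wording cannot stand. The directional hypothesis points one way and the decision rule the other, so the documents do not settle the matter.

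Two things are at stake. The first is whether the printed power describes the rule that will be applied. The second matters more: the same data could be reported as evidence of superiority or not, depending on a choice that the plan leaves open until after the data are seen.

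**Working it through.** **Inputs.** 25 per arm, 1:1 (sections 16.2 and 16.5); response rates, level and stated power (Table 16.51); chi-square or Fisher's exact test (section 16.31).

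**Step 1: reproduce the table.** With TENS rate p1, Scrambler rate p2, p̄ = (p1 + p2)/2 and n = 25, the pooled normal formula is

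power = Φ{ [ (p2 − p1) − z·√(2p̄(1 − p̄)/n) ] / √( [p1(1 − p1) + p2(1 − p2)]/n ) }.

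For row 2 (.10 against .40), p̄ = .25. The null standard error is √(.375/25) = .1225 and the alternative one is √(.33/25) = .1149.

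- One-sided, z = 1.645: (.30 − .2015)/.1149 = .858, so power is .80. The table says 80%.
- Two-sided, z = 1.960: (.30 − .2400)/.1149 = .522, so power is .70.

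The one-sided formula matches all five rows once results are cut to whole percents. Searched in steps of .01, it also returns the table's own detectable differences. The table is therefore not miscalculated.

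**Step 2: all rows at both levels.** Exact figures come from summing binomial probabilities over all 26 × 26 outcomes, using the uncorrected Pearson chi-square.

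| TENS / Scrambler | Table | Formula, one-sided | Formula, two-sided | Exact, one-sided | Exact, two-sided |
|---|---|---|---|---|---|
| .05 / .32 | 80% | 80.7% | 70.3% | 84.9% | 76.0% |
| .10 / .40 | 80% | 80.5% | 69.9% | 82.1% | 73.4% |
| .20 / .54 | 81% | 81.7% | 71.4% | 82.9% | 74.3% |
| .30 / .65 | 81% | 81.3% | 71.0% | 83.7% | 75.5% |
| .40 / .75 | 82% | 82.1% | 71.9% | 84.0% | 75.8% |

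No row reaches 80% two-sided by either method.

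**Step 3: detectable difference at 80% power, two-sided.** By the table's formula it is .32/.35/.38/.39/.39, and by exact chi-square .29/.33/.37/.37/.37.

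**Step 4: effect of Fisher's test.** The plan gives no switching rule, so assume that Fisher's test replaces chi-square when any expected count is below 5. This happens with probability .55 in row 1, .15 in row 2 and at most .002 in the others. Exact power is then .77/.80/.83/.84/.84 one-sided and .68/.72/.74/.75/.76 two-sided. The two-sided detectable differences are .32/.34/.37/.37/.37.

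**Step 5: where the conclusion turns.** Take 8 TENS and 14 Scrambler responders. The difference is .24 and p̄ = 22/50 = .44, so z = .24/√(.44 × .56 × 2/25) = .24/.1404 = 1.71. That gives p = .044 one-sided and .087 two-sided. With 15 Scrambler responders, z = 1.99 and two-sided p = .047.

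The pattern holds for every TENS count from 4 to 15. Six more responders (24 points) give p = .029 to .045 one-sided and .059 to .089 two-sided. Seven more (28 points) give two-sided p = .024 to .048. The smallest expected count is 7 for the six-responder cases and 6.5 for the seven-responder cases (15 against 22), so chi-square applies under the usual rule.

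**Step 6: the 30-point sentence.** Power for a 30-point difference at TENS rates .05/.10/.20/.30/.40:

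| Method | One-sided | Two-sided |
|---|---|---|
| Table's formula | .86/.80/.73/.70/.70 | .77/.70/.61/.57/.57 |
| Exact chi-square | .90/.82/.74/.73/.73 | .83/.73/.64/.62/.62 |

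Even one-sided, 80% is reached only at TENS rates of .05 and .10. The table itself asks for .34 to .35 at the higher rates.

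**The case against.** The strongest reply is that nothing is contradicted and only a convention is unstated. The table is labelled one-sided, is right at that level, and fits the directional hypothesis. A directional planning calculation can sit beside a two-sided analysis. The section disclaims confirmatory status, rests the sample size on feasibility, makes estimation the main purpose and reserves the p<0.05 clause for a very large difference. On this view, one phrase on sidedness would do.

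Much of that stands. The trial's size does not depend on the table, and reading the rule as two-sided is an inference from the either-arm wording and the chi-square test. The loose 30-point sentence is also partly corrected by the table beneath it. At a TENS rate of .05, the exact two-sided power for 30 points is above 80%.

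It does not remove the problem. Having disclaimed confirmation, the section still commits to a superiority conclusion at p<0.05, and feasibility justifies the number of patients rather than an undefined test. If chi-square is taken as two-sided by default, the printed power does not belong to it. If the test is one-sided, the reverse conclusion has to go.

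One possible charge should not be laid against the plan. It does not propose a one-sided 0.05 test in whichever direction the data point. Used that way with chi-square, type I error would be 9.9 to 11.9% at common response rates of .20 to .75. The ordinary two-sided chi-square is itself slightly above nominal there, at 5.4 to 6.5%.

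**Conclusion.** The concern holds. The table and the decision rule in section 16.5 do not match, and no section states the sidedness of the deciding p-value. If the rule is two-sided, the stated 80-82% power overstates the table's own calculation by about 10 points (70-72%) and exact chi-square power by about 5 to 8 points (73-76%). Over a wide range of plausible results, the open choice decides whether a 24-point advantage counts as evidence of superiority.

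The figures assume 25 evaluable patients per arm, the table's response rates and uncorrected chi-square, except where the assumed Fisher switch is named. The point should be fixed. It does not threaten the design, because the sample size is not derived from the table.

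**What to change.** **Preferred.** Keep the conclusion open to either arm. State in sections 16.31 and 16.5 that the p<0.05 rule is two-sided, and say when Fisher's test replaces chi-square, for example when any expected count is below 5. Restate Table 16.51 at two-sided 0.05. The simplest replacement uses the table's own formula: detectable improvements of .32/.35/.38/.39/.39. If exact calculation with that Fisher switch is preferred, they are .32/.34/.37/.37/.37.

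**Alternative.** Limit the p<0.05 conclusion to Scrambler superiority at one-sided 0.05, in line with Hypothesis 1, and delete the reverse conclusion. The table then stands for chi-square. With the Fisher switch only its first two rows move, to exact power of .77 and just under .80.

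**Either way**, replace the sentence about a 30% improvement with the power for a 30-point difference at each TENS rate.

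**Cost.** Two or three sentences and at most one table, with the sample size kept at 50. The two-sided option makes the detectable differences 4 to 5 points less favourable by the table's formula (3 to 4 points, exact against exact). The one-sided option gives up a p<0.05 conclusion in favour of TENS.
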